6.3. Assignment to Study Intervention

This is an open-label study with only 1 treatment.

6.4. Blinding

Not applicable as this is an open-label study with only 1 treatment.

6.5. Study Intervention Compliance

Study intervention will be administered under medical supervision by the investigator or designee. The dose of donanemab and study participant identification will be confirmed prior to the time of dosing. The date and time of each dose administered will be recorded in the source documents and in the case report form (CRF).

6.6. Dose Modification

Dose adjustments are not permitted in this study.

6.7. Continued Access to Study Intervention after the End of the Study

Not applicable.

6.8. Treatment of Overdose

In the event of an overdose, the investigator or treating physician should:

- contact the medical monitor immediately
- closely monitor the participant for any AE/ serious adverse event (SAE) and laboratory abnormalities, and
- obtain a plasma sample for PK analysis if requested by the medical monitor (determined on a case-by-case basis).

6.9. Prior and Concomitant Therapy

Any medication (including over-the-counter or prescription medicines, vitamins, and/or herbal supplements) or other specific categories of interest that the participant is receiving at the time of enrollment or receives during the study must be recorded along with:

- reason for use
- dates of administration including start and end dates, and
- dosage information including dose and frequency for concomitant therapy of special interest.

The medical monitor should be contacted if there are any questions regarding concomitant or prior therapy.

Participants must abstain from taking prescription or nonprescription drugs (including vitamins and dietary or herbal supplements) within 7 days (or 14 days if the drug is a potential enzyme inducer) or 5 half-lives (whichever is longer) before the start of study intervention until completion of the follow-up visit, unless, in the opinion of the investigator and sponsor, the medication will not interfere with the study.

Acetaminophen, at doses of ≤ 3 grams/day, is permitted for use in a 24-hour period at the discretion of the investigator. Other concomitant medication may be considered on a case-by-case basis by the investigator in consultation with the medical monitor if required. Any additional medication used during the course of the study must be documented.

COVID-19 Considerations

Government guidance for Health Facilities should be followed when conducting visits.

The use of a severe acute respiratory syndrome coronavirus 2 of the genus Betacoronavirus (SARS-CoV-2) vaccine in participants treated with donanemab has not been studied by Lilly. However, given the risk posed by coronavirus disease 2019 (COVID-19) in the midst of this pandemic, decisions regarding the use of any vaccination, including approved/authorized for use vaccines, in participants treated with donanemab should be made at the discretion of the treating physician using their best clinical judgment and after careful consideration of risk benefit factors for the participant. If you have any questions regarding the type of vaccine that can be used for your clinical study participants, please contact your Centers for Disease Control and Prevention (CDC) or medical monitor for further instructions. Please have information on the vaccine(s) available in your country, prior to contacting your medical monitor.

Please consult the vaccine product label for further information regarding associated risks and precautions, and guidance from your local regulatory agency. Hypersensitivity events have been reported in association with certain vaccines, in close temporal relation to the application. Taking this into consideration, it is recommended that study drug not be administered sooner than 5 days before or after a vaccination.

As with all other concomitant medications, please ensure you record applicable information regarding an individual's receipt of vaccination(s) in the participant's source documents, and then follow the CRF instructions for concomitant medications for appropriate capture of vaccine administration in the CRFs. Please record each administration date of the vaccine (each time) as a concomitant medication in the CRF. If the participant is vaccinated outside of your facility, please request and record information such as manufacturer and dose date, when available. Any possible related AEs from the vaccination should be reported according to the Lilly Adverse Event/Serious Adverse Event reporting guidance and to the appropriate manufacture, according to local practice.

7. Discontinuation of Study Intervention and Participant Discontinuation/Withdrawal

Participants discontinuing from the study prematurely for any reason must complete AE and follow-up procedures per Section 1.3 of this protocol.

Discontinuation of specific sites or of the study as a whole are handled as part of Appendix 1 (Section 10.1).

7.1. Discontinuation of Study Intervention

When necessary, a participant may be permanently discontinued from study intervention. If so, the participant will remain in the study and follow procedures for remaining study visits, as shown in the SoA. A participant should be permanently discontinued from study intervention if

- the participant becomes pregnant during the study,
- in the opinion of the investigator, the participant should permanently discontinue the study intervention for safety reasons
- if the investigator determines that a systemic hypersensitivity reaction has occurred related to study intervention administration, the participant may be permanently discontinued from the study intervention, and the sponsor's designated medical monitor should be notified. If the investigator is uncertain about whether a systemic hypersensitivity reaction has occurred and whether discontinuation of study intervention is warranted, the investigator may consult the sponsor.

In addition, study drug may be discontinued if participants

- answered “yes” to Question 4 or Question 5 on the “Suicidal Ideation” portion of the C-SSRS, or
- answered “yes” to any of the suicide-related behaviors on the Suicidal Behavior portion of the C-SSRS.

A psychiatrist or appropriately trained professional may assist in the decision to discontinue the participant.

7.1.1. Liver Chemistry Stopping Criteria

Discontinuation of the study intervention for abnormal liver tests **should be considered** by the investigator when a participant meets 1 of the following conditions after consultation with the Lilly designated medical monitor:

- ALT (alanine aminotransferase) or AST (aspartate aminotransferase) $>5\times$ for healthy participants upper limit of normal (ULN)
- ALT or AST $>3\times$ ULN for healthy participants sustained for more than 2 weeks or
- ALT or AST $>3\times$ ULN and total bilirubin level (TBL) $>2\times$ ULN or international normalized ratio (INR) >1.5 or
- ALT or AST $>3\times$ ULN the appearance of fatigue, nausea, vomiting, right upper-quadrant pain or tenderness, fever, rash, and/or eosinophilia ($>5\%$)
- alkaline phosphatase (ALP) $>3\times$ ULN

- ALP $>2.5 \times$ ULN and TBL $>2 \times$ ULN
- ALP >2.5 ULN with the appearance of fatigue, nausea, vomiting, right quadrant pain or tenderness, fever, rash, and/or eosinophilia ($>5\%$).

Participants who discontinue from study intervention due to the abnormal liver tests will undergo monitoring as described in Appendix 10.6.

Interrupting study drug based on liver test elevations in participants with normal or near-normal baseline liver tests

In study participants with normal or near normal baseline liver tests (ALT, AST, ALP $<1.5 \times$ ULN), the study drug should be **interrupted** and close hepatic monitoring initiated (see Section 8.2.8.1) if one or more of these conditions occur:

Elevation	Exception
ALT or AST $>5 \times$ ULN	
ALT or AST $>3 \times$ ULN and either TBL $>2 \times$ ULN or INR >1.5	For participants with Gilbert's syndrome: If baseline direct bilirubin is >0.5 mg/dL, then doubling of direct bilirubin should be used for drug interruption decisions rather than TBL $>2 \times$ ULN.
ALT or AST $>3 \times$ ULN with the appearance of fatigue, nausea, vomiting, right upper quadrant pain or tenderness, fever, rash, and/or eosinophilia ($>5\%$)	
ALP $>3 \times$ ULN, when the source of increased ALP is the liver	
ALP $>2.5 \times$ ULN and TBL $>2 \times$ ULN	For participants with Gilbert's syndrome: If baseline direct bilirubin is >0.5 mg/dL, then doubling of direct bilirubin should be used for drug interruption decisions rather than TBL $>2 \times$ ULN.
ALP $>2.5 \times$ ULN with the appearance of fatigue, nausea, vomiting, right upper quadrant pain or tenderness, fever, rash, and/or eosinophilia ($>5\%$)	

Abbreviations: ALP = alkaline phosphatase; ALT = alanine aminotransferase; AST = aspartate aminotransferase; INR = international normalized ratio; TBL = total bilirubin; ULN = upper limit of normal.

Source: [FDA] United States Food and Drug Administration. Drug-induced liver injury: premarketing clinical evaluation: guidance for industry. July 2009. Accessed August 26, 2022.
<https://www.fda.gov/media/116737/download>

Interrupting study drug based on elevated liver tests in participants with abnormal baseline liver tests

In study participants with abnormal baseline liver tests (ALT, AST, ALP $\geq 1.5 \times$ ULN), the study drug should be **interrupted** if one or more of these conditions occur:

Elevation	Exception
ALT or AST $>3 \times$ baseline	
ALT or AST $>2 \times$ baseline and either TBL $>2 \times$ ULN or INR >1.5	For participants with Gilbert's syndrome: If baseline direct bilirubin is >0.5 mg/dL, then doubling of direct bilirubin should be used for drug interruption decisions rather than TBL $>2 \times$ ULN.
ALT or AST $>2 \times$ baseline with the appearance of fatigue, nausea, vomiting, right upper quadrant pain or tenderness, fever, rash, and/or eosinophilia ($>5\%$)	
ALP $>2.5 \times$ baseline, when the source of increased ALP is the liver	
ALP $>2 \times$ baseline and TBL $>2 \times$ ULN	For participants with Gilbert's syndrome: If baseline direct bilirubin is >0.5 mg/dL, then doubling of direct bilirubin should be used for drug interruption decisions rather than TBL $>2 \times$ ULN.
ALP $>2 \times$ baseline with the appearance of fatigue, nausea, vomiting, right upper quadrant pain or tenderness, fever, rash, and/or eosinophilia ($>5\%$)	

Abbreviations: ALP = alkaline phosphatase; ALT = alanine aminotransferase; AST = aspartate aminotransferase; INR = international normalized ratio; TBL = total bilirubin; ULN = upper limit of normal.

Source: [FDA] United States Food and Drug Administration. Drug-induced liver injury: premarketing clinical evaluation: guidance for industry. July 2009. Accessed August 26, 2022.
<https://www.fda.gov/media/116737/download>

Resuming study drug after elevated liver tests

Resumption of the study drug can be considered only in consultation with the Lilly-designated medical monitor and only if the liver test results return to baseline and if a self-limited nondrug etiology is identified. Otherwise, the study drug should be discontinued.

7.2. Participant Discontinuation/Withdrawal from the Study

Discontinuation is expected to be uncommon.

A participant may withdraw from the study:

- at any time at the participant's own request
- at the request of the participant's designee (eg, parents or legal guardian)
- at the discretion of the investigator for safety, behavioral, compliance, or administrative reasons

- if enrolled in any other clinical study involving an investigational product, or enrolled in any other type of medical research judged not to be scientifically or medically compatible with this study
- if the participant, for any reason, requires treatment with a therapeutic agent that is prohibited by the protocol and has been demonstrated to be effective for treatment of the study indication. In this case, discontinuation from the study occurs prior to introduction of the new agent.

At the time of discontinuing from the study, if possible, the participant will complete procedures for an early discontinuation visit, as shown in the SoA. If the participant has not already discontinued the study intervention, the participant will be permanently discontinued from the study intervention at the time of the decision to discontinue the study.

If the participant withdraws consent for disclosure of future information, the sponsor may retain and continue to use any data collected before such a withdrawal of consent. If a participant withdraws from the study, the participant may request destruction of any samples taken and not tested, and the investigator must document this in the site study records.

7.3. Lost to Follow up

A participant will be considered lost to follow-up if he or she repeatedly fails to return for scheduled visits and is unable to be contacted by the study site. Site personnel or designee are expected to make diligent attempts to contact participants who fail to return for a scheduled visit or were otherwise unable to be followed up by the site.

Site personnel, or an independent third party, will attempt to collect the vital status of the participant within legal and ethical boundaries for all participants randomized, including those who did not get investigational product. Public sources may be searched for vital status information. If vital status is determined to be deceased, this will be documented and the participant will not be considered lost to follow-up. Sponsor personnel will not be involved in any attempts to collect vital status information.

8. Study Assessments and Procedures

- Study procedures and their timing are summarized in the SoA.
- Immediate safety concerns should be discussed with the sponsor immediately upon occurrence or awareness to determine if the participant should continue or discontinue study intervention.
- Adherence to the study design requirements, including those specified in the SoA, is essential and required for study conduct.
- All screening evaluations must be completed and reviewed to confirm that potential participants meet all eligibility criteria. The investigator will maintain a screening log to record details of all participants screened and to confirm eligibility or record reasons for screening failure, as applicable.
- Section 1.3 lists the SoA, detailing the study procedures and their timing (including tolerance limits for timing). The specifications in this protocol for the timings of safety and sample collection are given as targets to be achieved within reasonable limits. Modifications may be made to the time points based upon emerging clinical information. The scheduled time points may be subject to minor alterations; however, the actual time must be correctly recorded.
- Appendix 10.2 lists the laboratory tests that will be performed for this study.
- Appendix 10.2.1 provides a summary of the maximum number and volume of invasive samples, for all sampling, during the study.
- Unless otherwise stated in subsections below, all samples collected for specified laboratory tests will be destroyed within 60 days of receipt of confirmed test results. Certain samples may be retained for a longer period, if necessary, to comply with applicable laws, regulations, or laboratory certification standards.

8.1. Efficacy Assessments

Not applicable.

8.2. Safety Assessments

Planned time points for all safety assessments are provided in the SoA.

8.2.1. Physical Examinations

- A complete physical examination will include, at a minimum, assessments of the cardiovascular, respiratory, gastrointestinal, and neurological systems. Height and weight will also be measured and recorded.
- Symptom-directed physical assessment may be conducted at other visits as mentioned in SoA and as clinically indicated. Symptom-directed physical examinations may also be conducted at other visits, as determined by the investigator, if a participant presents with complaints.

- Investigators should pay special attention to clinical signs related to previous serious illnesses.

8.2.2. Vital Signs

- For each participant, vital signs measurements should be conducted according to the SoA (Section 1.3).
- Additional vital signs may be measured during the study if warranted.
- Blood pressure and pulse rate should be measured after at least 5 minutes supine.
- Unscheduled orthostatic vital signs should be assessed if possible, during any AE of dizziness or posture-induced symptoms. If orthostatic measurements are required, participants should be supine for at least 5 minutes and stand for at least 3 minutes. If the participant feels unable to stand, only the supine vital signs will be recorded.
- Body temperature should be measured as indicated in the SoA, or any time that it is clinically indicated.

8.2.3. Electrocardiograms

- Single 12-lead ECG will be obtained as outlined in the SoA (see Section 1.3) using an ECG machine that automatically calculates the heart rate and measures PR, QRS, QT, and corrected QT interval (QTc).
- For each participant, ECGs should be collected according to the SoA (Section 1.3).
- Any clinically significant findings from ECGs that result in a diagnosis and that occur after the participant receives the first dose of the investigational product, should be reported to Lilly, or its designee, as an AE via the eCRF.
- Electrocardiograms must be recorded before collecting any blood samples. Participants must be supine for approximately 5 to 10 minutes before ECG collection and remain supine but awake during ECG collection. Electrocardiograms may be obtained at additional times, when deemed clinically necessary. All ECGs recorded should be stored at the investigational site.
- Electrocardiograms will be interpreted by a qualified physician (the investigator or qualified designee) as soon after the time of ECG collection as possible, and ideally while the participant is still present, to determine whether the participant meets entry criteria at the relevant visit(s) and for immediate participant management, should any clinically relevant findings be identified.

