8.3.1. Timing and Mechanism for Collecting Events

This table describes the timing, deadlines, and mechanism for collecting events.

Event	Collection Start	Collection Stop	Timing for Reporting to Sponsor or Designee	Mechanism for Reporting	Back-up Method of Reporting
Adverse Event					
AE	signing of the informed consent form (ICF)	participation in study has ended	As soon as possible upon site awareness	AE CRF	N/A
Serious Adverse Event					
SAE and SAE updates – prior to start of study intervention and deemed reasonably possibly related to study procedures	signing of the ICF	start of intervention	Within 24 hours of awareness	SAE paper form	SAE paper form
SAE and SAE updates – after start of study intervention	start of intervention	participation in study has ended	Within 24 hours of awareness	SAE paper form	SAE paper form
SAE ^a – after participant's study participation has ended and the investigator becomes aware	After participant's study participation has ended	N/A	Promptly	SAE paper form	N/A
Pregnancy					
Pregnancy in female participants and female partners of male participants	After the start of study intervention	60 days following the after final dose	Within 24 hours (see Section 8.3.2)	Pregnancy paper form	Pregnancy paper form

Event	Collection Start	Collection Stop	Timing for Reporting to Sponsor or Designee	Mechanism for Reporting	Back-up Method of Reporting
Product Complaints					
PC associated with an SAE or might have led to an SAE	Start of study intervention	End of study intervention	Within 24 hours of awareness	Product Complaint form	N/A
PC not associated with an SAE	Start of study intervention	End of study intervention	Within 1 business day of awareness	Product Complaint form	N/A
Updated PC information	—	—	As soon as possible upon site awareness	Originally completed Product Complaint form with all changes signed and dated by the investigator	N/A
PC (if investigator becomes aware)	Participation in study has ended	N/A	Promptly	Product Complaint form	

Abbreviations: AE = adverse event; ICF = informed consent form; N/A = not applicable; PC = product complaints; SAE = serious adverse event.

a Serious adverse events should not be reported unless the investigator deems them to be possibly related to study treatment or study participation.

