9.3.5.2. Statistical Evaluation of Safety

All study intervention and protocol procedure AEs and SAEs will be listed, and if the frequency of events allows, safety data will be summarized using descriptive methodology. The incidence of symptoms will be presented by severity and by association with the study intervention as perceived by the investigator. Symptoms reported to have occurred prior to randomization will be distinguished from those reported as new or increased in severity during the study. Each symptom will be classified by the most suitable term from the Medical Dictionary for Regulatory Activities. The number of AEs and SAEs will be reported.

Safety parameters that will be assessed include safety laboratory parameters, vital signs, and ECG parameters. The safety parameters will be listed and summarized using standard descriptive statistics. Additional analysis will be performed if warranted upon review of the data.

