10.3.1. Definition of AE

AE Definition

- An AE is any untoward medical occurrence in a participant administered a pharmaceutical product and which does not necessarily have a causal relationship with the study intervention. An AE can therefore be any unfavourable and unintended sign (including an abnormal laboratory finding), symptom, or disease (new or exacerbated) temporally associated with the use of a medicinal (investigational) product, whether or not related to the medicinal (investigational) product.

Events Meeting the AE Definition

- Any abnormal laboratory test results (hematology, clinical chemistry, or urinalysis) or other safety assessments (for example, ECG, radiological scans, vital signs measurements), including those that worsen from baseline, considered clinically significant in the medical and scientific judgment of the investigator (that is, not related to progression of underlying disease).
- Exacerbation of a chronic or intermittent pre-existing condition including either an increase in frequency and/or intensity of the condition.
- New condition detected or diagnosed after study intervention administration even though it may have been present before the start of the study.
- Signs, symptoms, or the clinical sequelae of a suspected drug-drug interaction.
- Medication error, misuse, or abuse of IMP, including signs, symptoms, or clinical sequelae.

Events NOT Meeting the AE Definition

- Any clinically significant abnormal laboratory findings or other abnormal safety assessments that are associated with the underlying disease, unless judged by the investigator to be more severe than expected for the participant's condition.
- The disease/disorder being studied or expected progression, signs, or symptoms of the disease/disorder being studied, unless more severe than expected for the participant's condition.
- Medical or surgical procedure (for example, endoscopy, appendectomy): the condition that leads to the procedure is the AE.
- Situations in which an untoward medical occurrence did not occur (social and/or convenience admission to a hospital).

- Anticipated day-to-day fluctuations of pre-existing disease(s) or condition(s) present or detected at the start of the study that do not worsen.

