10.4.5 Electrocardiogram (ECG)

ECGs will be performed for safety monitoring purposes only and will not be presented. Any clinically significant findings from ECGs will be reported as an AE.

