12. CHANGES FROM THE PROTOCOL SPECIFIED STATISTICAL ANALYSES

There were no changes from the protocol specified statistical analyses.

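### Protocol 8.2.3 ties AE reporting of ECG findings to a diagnosis while Appendix 3 and SAP 10.4.5 do not, so a clinically significant, undiagnosed finding could drop out of the TEAE count and every planned output

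*Protocol*

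**What the plan says.** Three places state when an ECG finding becomes an adverse event.

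- Protocol 8.2.3, the ECG section, directs sites to report as AEs "Any clinically significant findings from ECGs that result in a diagnosis and that occur after the participant receives the first dose" of investigational product.
- Protocol 10.3.1 (Appendix 3), which section 8.3 names as the home of the AE definition, covers abnormal laboratory results "or other safety assessments (for example, ECG, radiological scans, vital signs measurements), including those that worsen from baseline, considered clinically significant" by the investigator. It names ECG and sets no diagnosis condition.
- SAP 10.4.5 states: "Any clinically significant findings from ECGs will be reported as an AE". It too sets no diagnosis condition.

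On ECG outputs the two documents differ. Protocol 9.3.5.2 says "Safety parameters that will be assessed include safety laboratory parameters, vital signs, and ECG parameters", and adds that these parameters will be listed and summarized. SAP 10.4.5 says "ECGs will be performed for safety monitoring purposes only and will not be presented". SAP section 12 nevertheless records: "There were no changes from the protocol specified statistical analyses".

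The only secondary endpoint is the incidence of TEAEs and SAEs (protocol section 3, SAP section 4). Under SAP 10.4.1 an event must be an AE before it can be a TEAE.

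**The concern.** The instruction that site staff are most likely to consult when they handle an ECG is narrower than both the general AE definition and the rule the SAP relies on. Two investigators could each point to protocol text and record the same tracing differently.

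This would matter less if ECG data were reported separately. As the SAP stands, the AE record is the only stated route from an ECG to the study results, and 8.2.3 can be read as narrowing that route. At stake is the completeness of the secondary safety endpoint, together with an undeclared loss of the ECG output that the protocol describes.

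**Working it through.** The plan gives no figure to reproduce, so the check compares the texts and traces the consequence.

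**1. The rules side by side**

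- Protocol 8.2.3: clinically significant, and leading to a diagnosis, and after the first dose.
- Protocol 10.3.1: clinically significant in the investigator's judgment.
- SAP 10.4.5: clinically significant.

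Every finding that meets 8.2.3 also meets the other two. The reverse is not true, so applying 8.2.3 alone can remove AEs but never add them.

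**2. Is the diagnosis clause only a naming convention?** Protocol 10.3.4 asks that, where possible, the diagnosis be documented in place of the individual signs or symptoms. That governs what an AE is called, and it allows for AEs without a diagnosis. In 8.2.3 the diagnosis is part of the description of what is to be reported. The neighbouring laboratory section (8.2.4) asks for clinically relevant changes to be reported as AEs without any such condition.

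**3. Effect on the endpoint.** Take a participant whose only event is a post-dose ECG finding judged clinically significant but given no diagnosis.

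- Under 10.3.1 and SAP 10.4.5 it is an AE, hence a TEAE under SAP 10.4.1, and the participant is counted.
- Under 8.2.3 read alone, it is not entered, so the participant is not counted.

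If the participant has another TEAE, participant-level incidence is unchanged, but the count of events falls by one.

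**4. The first-dose clause.** Under SAP 10.4.1 a pre-dose finding is treatment-emergent only if it becomes more severe post-dose, and that worsening itself falls after the first dose. The clause therefore removes no TEAE. It does sit awkwardly with section 8.3.1, which starts AE collection at "signing of the informed consent form (ICF").

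**5. Other routes to the report.** Protocol 8.2.3 keeps the tracings at the site. SAP 10.1 promises listings of all databased data, but the specific ECG statement in 10.4.5 excludes ECGs. The catch-all listing in SAP 10.4.12 applies only to assessments not otherwise detailed. Under protocol 8.2.8 the sponsor reviews ECGs periodically, but that is monitoring and not a planned output.

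**6. Scale.** The Schedule of Activities places an ECG before dosing on Day 1 of each period and another on Day 96. After the first dose that is 5 (Periods 2 to 6) + 1 (Day 96) = 6 per completer.

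- 25 completers: 6 × 25 = 150 ECGs.
- All 40 enrolled complete: 6 × 40 = 240 ECGs, an upper limit for scheduled tracings.

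If x participants among N treated are missed and have no other TEAE, incidence falls by 100·x/N percentage points. With N = 40 and x = 1 this is 100 × 1/40 = 2.5 points. With x = 0 it is zero. The documents give no value for x.

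**The case against.** The strongest reply is that 8.2.3 does not say a diagnosis is the only way an ECG finding becomes an AE. It can be read as a sufficient condition. Section 8.3 makes investigators responsible for recording events that meet the Appendix 3 definitions, and Appendix 3 names ECG. A site that applies 10.3.1 would report the finding, and one that omitted it would depart from 8.3. This stands. The loss arises only where a site treats 8.2.3 as governing, which is a reasonable reading of a specific instruction but not the only one. It is also fair that the documents do not define a diagnosis, so how many findings would fall into the gap is uncertain.

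A reader might infer more than the text supports in two ways. One is that the first-dose clause also causes undercounting; step 4 shows that it does not. The other is to express the effect per 25 completers, which would make each participant worth 4 points (1/25). That is the wrong denominator, because protocol 9.3.1 bases safety analyses on all enrolled participants who received study intervention, whether or not they completed.

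Finally, the study is single-arm and descriptive, with no hypothesis test, and enrols healthy adults aged 18 to 40 with clinically significant ECG abnormalities excluded. The expected number of such findings is probably small. This limits the importance of the point but does not remove the contradiction.

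**Conclusion.** The three passages set different thresholds, and the SAP leaves no other planned output in which a missed ECG finding would show. The secondary TEAE incidence is therefore exposed to an undercount and, from this source, to no overcount. An actual undercount is not demonstrated. It requires a clinically significant, undiagnosed, post-dose finding and a site that follows 8.2.3 in preference to 10.3.1. The number of affected participants cannot be estimated from the documents and may be zero. On the assumption that 40 are treated, each one with no other TEAE is worth 2.5 points.

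The linked conflict over ECG outputs, between protocol 9.3.5.2 and SAP 10.4.5, is definite and undeclared. SAP section 3 lets the SAP supersede the protocol's statistical considerations but says substantial differences will be identified, and section 12 identifies none. The point is worth correcting because the remedy costs very little, not because a large effect is expected.

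**What to change.** 1. In protocol 8.2.3, delete the condition that the finding lead to a diagnosis, or replace it with a cross-reference to 10.3.1. Any ECG finding the investigator judges clinically significant is then recorded as an AE, under the diagnosis if there is one and otherwise as the finding itself.
2. Reconcile SAP 10.4.5 with protocol 9.3.5.2. Either list the ECG data, or keep the omission and declare it as a change in SAP section 12. A listing would also give a second route by which ECG findings could reach the report.
3. The first-dose clause need not be deleted to protect the TEAE endpoint. Aligning it with AE collection from consent is optional tidying.

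The cost is a one-sentence protocol clarification, a site reminder, and either an ECG listing or a one-line entry in SAP section 12. There are no new procedures. The downside is possibly a few more AE entries.
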